Hospital length of stay will be collected from medical records and be defined as the number of days from surgical admission to hospital discharge.

Hospital readmission will be assessed as whether a patient is rehospitalized in an unplanned response to a surgical complication within 30 days of hospital discharge. Planned rehospitalizations will not be assessed as a hospital readmission.

Hospital physical function will be assessed using the AM-PAC test of inpatient physical activity and basic mobility³⁰.

Questionnaire/Psychological Outcomes Assessment:

Fatigue will be assessed using the Functional Assessment of Chronic Illness Therapy - Fatigue scale (FACIT-Fatigue), a validate measure of fatigue in cancer survivors³¹.

Health-related Quality of Life (HRQOL) will be assessed with the Functional Assessment of Cancer Therapy-General form (FACT-G)³². This form provides information on the physical, social, emotional, and functional well-being of patients with cancer.

Subjective psychological stress will be assessed with the Perceived Stress Scale (PSS)³³, which assesses *perceived stress* based on individual and environmental stressful events, focusing on experiences in the last month. *Depression* will be assessed using the Center for Epidemiologic Studies Depression Scale (CES-D)³⁴.

Prior physical activity level will be assessed with the Godin Physical Activity Questionnaire. This measure is a self-report estimate of leisure physical activity for the prior month. Prior physical activity level will be compared between groups and considered as a potential factor to control for in statistical analyses. This will only be collected at the first assessment.

Objective Stress Assessment:

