The potential participant population will be individuals who receive a diagnosis of borderline-resectable pancreatic cancer (adenocarcinoma), being treated at the University Hospital Cancer Center. These inclusion and exclusion criteria will apply to participants in both groups.

Inclusion Criteria: Recent (< 4 week) first diagnosis of a borderline-resectable pancreatic adenocarcinoma, assigned to receive neoadjuvant therapy and surgery at University of Colorado Cancer Center, physician clearance to participate in exercise program, and age 21-80 years.

Exclusion Criteria: Any significant comorbid conditions that would interfere with or preclude participation in an exercise intervention, including orthopedic conditions such as advanced osteoarthritis, mobility-limiting amputations or chronic injuries, or mobility-limiting acute orthopedic injuries; advanced rheumatoid arthritis; widespread chronic pain conditions such as fibromyalgia; pulmonary conditions such as chronic obstructive pulmonary disease, emphysema, interstitial lung disease, use of supplemental oxygen; known cardiovascular disease, uncontrolled hypertension, or new cardiac event within the past 6 months. Participants with a second cancer diagnosis at the time of enrollment will be excluded.

Sample size estimation: No studies have previously investigated the effects of preoperative exercise in patients with pancreatic cancer. In patients with lung cancer, a preoperative exercise program reduced hospital length of stay by 4 days compared to usual care⁴⁰. Based on this difference, with a SD of 3, 12 participants would be required in each the experimental and control groups ($\alpha = 0.05$, $\beta = 0.90$ ⁴¹). To account for overall attrition, groups will be increased by 3 participants each, based on a study of preoperative exercise after neoadjuvant treatment in patients with rectal cancer showing an overall attrition of 28%⁴². A total of **30 participants (15 per group)** will be recruited for this study.

C. Study Design and Research Methods

This is a prospective, non-randomized, parallel group, intervention control trial, patterned on a similar pilot study in patients with rectal cancer⁴².

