Recruitment: Participants will be recruited from the University Hospital Cancer Center. Patients with a recent diagnosis (< 4 weeks) of pancreatic cancer will be given information on the study by their treating physicians and asked if they would be interested in participating. If yes, physicians will have patients complete a HIPAA A form to provide study personnel with their name. Study personnel will access the patients' medical records to evaluate the inclusion/exclusion criteria. If these criteria are met, research personnel will meet with the

potential participant at the University of Colorado Cancer Center to provide information about the study. If patients are still interested in participating, the familiarization and possibly first visit will be scheduled. Participants will have the option of combining the familiarization session and Visit 1. All data collected during screening will be destroyed and recollected after obtaining written consent in patients choosing to participate. If the inclusion/exclusion criteria are not met after review of the health record, the patient will be contacted and the exclusion decision will be explained.

Group Assignment: Volunteers meeting the inclusion and exclusion criteria and willing to participate in the exercise intervention will be assigned to the exercise group. The standard of care, non-exercise control group will comprise volunteers who meet the inclusion and exclusion criteria but are unable to commit to participation in the exercise intervention for practical reasons (e.g. barriers in transportation or home location). The use of a non-randomized study design is to maximize patients participating in the exercise program to determine accrual rate, program adherence, and safety while still allowing a non-exercise control group.

Protocol:

[figure not shown]

Figure 1

Figure 1 shows the event timeline of the study, with time points of visits and intervention in relation to diagnosis and surgery. Written informed consent will be obtained by a study investigator during a familiarization period, where participants will have assessments and the exercise investigation explained in-depth. There will be four time points for data collection: pre-intervention (Visit 1), post-intervention and preoperative (Visit 2), 30-day postoperative (data retrieved from electronic health record), and follow-up (Visit 3).

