The timeline for this protocol is estimated at 2 years. Data collection (participant recruitment and intervention) is estimated at 1 - 1.5, after which data will be analyzed and manuscripts prepared.

Data Analysis and Anticipated Outcomes: Groups will be compared on demographic variables such as age and gender. Variables that differ significantly will be included in planned analyses as covariates. Statistical significance will be defined as $\alpha \leq 0.05$, however, results will be interpreted cautiously as is warranted for pilot studies⁴⁴. As we expect to be underpowered to test for statistical interactions, multiple tests will be used to assess differences in baseline measures, change scores, and postoperative outcomes between groups. Change scores will be calculated as the difference between Visit 2 and Visit 1. Groups will be compared using non-parametric exact k-sample permutation tests, which are well suited for small sample sizes as they do not rely on typical normal-theory methods⁴⁵.

Aim 1: The feasibility of implementing this intervention will be assessed by quantifying the accrual rate of patients willing and able to participate in the preoperative exercise intervention and individual patients' adherence to the prescribed exercise program (percentage of scheduled sessions attended). Safety will be determined by the number of non-serious and serious adverse events and relatedness of the events to exercise, as described by COMIRB.

Aim 2: Hypothesis 1 – Baseline physical fitness and function measures and change scores will be compared between groups using exact k-sample permutation tests. We anticipate a significant difference in the changes from Visit 1 to Visit 2, with the Exercise group demonstrating maintained or improved physical fitness and function compared to the Control group, with no differences in baseline measures. A secondary analysis will be used to describe the trajectory of changes in physical function from visits 1, 2, and 3.

Hypothesis 2 – Postoperative outcomes will be compared with exact k-sample permutation tests (hospital length of stay) or Fisher's exact tests (hospital readmission) between the Exercise and Control groups. We anticipate the Exercise group to have a significantly lower hospital length of stay and occurrence of hospital readmission compared to the Control group.

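### Control assignment can depend on transport and home location, and length of stay counts every day from admission to discharge, so access delays could pass for an exercise benefit

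*Combined protocol and SAP*

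**What the plan says.** - **Design.** Section IV.C describes a "prospective, non-randomized, parallel group, intervention control trial". Under Group Assignment, eligible volunteers "willing to participate in the exercise intervention will be assigned to the exercise group". Controls are eligible volunteers who are "unable to commit to participation in the exercise intervention for practical reasons (e.g. barriers in transportation or home location").
- **Outcome.** Section IV.A, Postoperative outcomes, takes length of stay from the medical record, "defined as the number of days from surgical admission to hospital discharge". No version starts at the operation or ends when the patient is medically ready to leave. Aim 2 in section I refers to postoperative stay.
- **Sample size.** Section IV.B rests on length of stay: in lung cancer, "a preoperative exercise program reduced hospital length of stay by 4 days compared to usual care". It continues: "Based on this difference, with a SD of 3", "12 participants would be required in each the experimental and control groups".
- **Analysis.** Section IV.F compares stay between groups with an exact permutation test and expects it to be shorter with exercise. On adjustment it says: "Groups will be compared on demographic variables such as age and gender". Variables that differ significantly become covariates. Section IV.A adds prior physical activity as a possible control variable. Section IV.E tests the durations of exercise and neoadjuvant therapy as covariates, but only for fitness, function and stress outcomes.
- **Limitation stated.** Section IV.E accepts possible selection bias and baseline differences in general terms. It does not connect the assignment rule to length of stay.
- **Data not planned.** No section plans to record distance, travel, home support or the reason a volunteer became a control.

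**The concern.** In a non-randomized comparison, the most troublesome allocation variable is one that can act on the outcome by a route other than the treatment. Access to the hospital may be such a variable here. The plan itself gives it as an example of why someone becomes a control, and both ends of the length-of-stay interval are open to it. A patient from far away might be admitted before the day of surgery, or might wait for transport or home arrangements once fit to leave. Neither delay says anything about recovery, yet each counts as a day of outcome.

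If this happens more often among controls, it produces a shorter stay with exercise, which is what Aim 2, Hypothesis 2 predicts. Because distance and reason for assignment are not planned data, a reader of the results could not judge how much of a difference came from access.

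**Working it through.** **1. The plan's own figure.** Inputs from section IV.B: difference 4 days, SD 3, alpha 0.05, and 0.90, which is labelled beta but read here as power. Sidedness is not stated. Taking it as two-sided, with the normal approximation:

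n per group = 2 × [SD × (z₀.₉₇₅ + z₀.₉₀) / difference]² = 2 × [3 × (1.960 + 1.282) / 4]² = 11.82, rounded up to 12.

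This matches the plan. One-sided gives 10, so two-sided is used below.

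**2. Difference needed for significance.** With 12 per group the standard error of the difference is 3 × √(2/12) = 1.225 days. The critical t on 22 degrees of freedom is 2.074, so an observed difference of 2.074 × 1.225 = 2.54 days is significant. With 15 per group it is 2.048 × 1.095 = 2.24 days. One spurious day is therefore 1/2.54 = 39% of the threshold at 12 per group, and 1/4 = 25% of the planned effect.

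**3. False-positive rate under an assumed access excess.** The documents give no size for such a delay, so the range of b is an assumption. Suppose exercise has no effect and control stays are longer by b days on average. The t statistic then has noncentrality b / 1.225 (12 per group) or b / 1.095 (15 per group).

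| b (days) | Noncentrality, 12 per group | Two-sided rate, 12 per group | Of which favouring exercise | Two-sided rate, 15 per group |
|---|---|---|---|---|
| 0 | 0 | 5.0% | 2.5% | 5.0% |
| 0.5 | 0.408 | 6.8% | 5.8% | 7.3% |
| 1 | 0.816 | 12.2% | 11.9% | 14.3% |
| 2 | 1.633 | 35% | 35% | 42.2% |

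**4. Check with the planned type of test.** A simulated two-sided permutation test (12 per group, 3,000 runs, 999 permutations each) gave significant results favouring exercise in 2.4%, 11.3% and 34.6% of runs at b = 0, 1 and 2. When half the controls were delayed by 2 days (mean 0.5 × 2 = 1 day), the figure was 11.4%. The t-based figures are adequate for the planned test.

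**5. What a mean of 1 day would require.** One route is that half the controls have one extra night before surgery and one extra day before discharge, and no exercise patient has either: 0.5 × (1 + 1) = 1 day. Counting from the operation would remove the first part and leave 0.5 × 1 = 0.5 day, which takes the two-sided rate from 12.2% to 6.8%.

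**6. Would the existing covariate rule catch it?** Only if distance were recorded and treated as one of the demographic variables. Even then, a group imbalance of 0.5 SD would be declared significant only 22% of the time with 12 per group and 26% with 15.

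**7. Cost of adjusting for distance.** With a true 4-day effect, SD 3 and 12 per group, unadjusted t-test power is 88% (noncentrality 4/1.225 = 3.27). If distance correlates r with group, the noncentrality is multiplied by √(1 − r²), with 21 degrees of freedom. For assumed r of 0.7, 0.8 and 0.9 it becomes 2.33, 1.96 and 1.42, and power falls to about 60%, 46% and 27%. An adjusted analysis cannot reasonably be made a condition for the claim.

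**The case against.** Several points against the concern are sound.

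- Transport and home location are examples. The commitment is three sessions a week, typically on weekdays between 8AM and 4PM (section IV.C), so work or caring duties could put a patient who lives nearby in the control group. The share of controls with access barriers is unknown. A reader might infer that distance alone decides the group; the text does not say so.
- Everyone is due to receive neoadjuvant therapy and surgery at the same centre and attends three visits at the same site. Patients with the worst access problems may not enrol, which would narrow the contrast.
- Nothing in the documents shows that remote patients are admitted early or discharged late. The effect could be negligible, or reversed if distant patients are transferred elsewhere sooner. A reader might conclude that the bias favours exercise; the documents support only that it could.
- The plan already concedes selection bias (section IV.E) and promises cautious interpretation as a pilot (section IV.F). It chose this design to study accrual, adherence and safety.
- It would be too strong to say that no analysis could deal with the effect. The demographic covariate list is open-ended, and the health record is to be reviewed for length of stay anyway.

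These points limit the certainty and size of the concern. They leave one gap: the general admission of selection bias does not identify this route into the outcome used for sample size, and the plan collects nothing with which to examine it.

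**Conclusion.** The concern holds as a possibility that the plan should be able to examine. It is not a demonstrated bias. The allocation rule and the outcome definition share a potential common cause, access to the hospital, and the outcome as defined includes preoperative days that Aim 2 does not ask about. An average control excess of 1 day would more than double the nominal 5% error rate, to 12%, and 2 days would take it to 35%; at 0.5 day the change is small, to 6.8%. These figures assume no true effect, the plan's SD of 3 days, 12 evaluable patients per group, and an excess confined to controls. The excess itself is assumed throughout.

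The documents do not support the stronger conclusion that a shorter stay with exercise would be uninterpretable. They do support a low-cost change of definition and a few added data items.

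**What to change.** 1. Define the length-of-stay outcome as days from the date of operation to discharge, and report admission-to-discharge as secondary. This matches Aim 2 and removes any preoperative nights.
2. Record home-to-hospital distance for every participant, record the reason for control assignment at enrolment, and report distance by group. The reason exists only for controls, so it is descriptive and cannot be a covariate.
3. Prespecify two sensitivity analyses: one adjusted for distance whatever its baseline p-value, and one ending at the first date the chart records the patient as medically ready to leave, where that date is available. State how the covariate enters the permutation test, for example by permuting residuals. Do not make agreement of these analyses a condition for the claim.
4. Describe the length-of-stay comparison as an association that may partly reflect access.

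The cost is one change of definition and a few extra fields, mostly collected at the record review already planned 30 days after discharge. Some readiness dates will be missing, and adjustment will be imprecise if distance nearly separates the groups. The change of start date does not deal with delays at discharge; only the sensitivity analyses bear on those.

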No preliminary studies have been carried out examining preoperative exercise in patients with pancreatic cancer. The preoperative exercise intervention, however, will be administered through the BFitBWell Cancer and Exercise Program at the Anschutz Health and Wellness Center. This program has successfully provided individualized exercise interventions to over 100 cancer survivors during the past two years. These interventions are led by trained cancer and exercise specialists, and have led to consistent improvements in physical fitness, physical function, and quality of life.

The BFitBWell program has provided exercise interventions for six patients with pancreatic cancer. Pre- and post-program measures of physical fitness were collected in two of these patients, both showing improvement. Measures of strength and physical function improved in the majority of patients and 4 of 6 patients reported measurable decreases in fatigue.

Based on discussions with physicians at the University of Colorado Cancer Center, approximately 100 patients are diagnosed and treated there each year who would be potential participants in the proposed study.

IV. Research Methods

A. Outcome Measure(s):

Physical fitness and function outcomes:

The primary outcome of physical fitness and function will be the *400-meter walk time*, which is a validated measure of cardiorespiratory fitness and mobility. The test assesses the time it takes a participant to independently walk 400 meters¹⁵. This test was developed to assess functional walking and exercise capacity in older adults, as distance was found to be more motivating than time (compared to the 6 minute walk test). This test has been associated with the development of cardiovascular disease and functional limitations¹⁶, and has been used to assess functional walking and exercise capacity in cancer populations¹⁷.

Secondary measures of physical fitness and function include:

Lean muscle mass and body composition. This will be assessed utilizing a dual-energy x-ray absorptiometry (DXA) scan. This is the gold standard measure of body composition and commonly used in studies of exercise interventions in cancer survivors¹⁸. The potential preservation of lean muscle is an important assessment in this population as improved muscle quantity and quality has been associated with improved postoperative outcomes in patients with pancreatic cancer undergoing surgery¹⁹.

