Assessments: All assessments will be performed at the Anschutz Health and Wellness Center. Participants will also complete the Godin Physical Activity Questionnaire during Visit 1 only. The following assessments will be completed at visits 1, 2, and 3.

A total body DXA scan will be performed to determine body composition. The scan takes approximately 3 minutes, but 15 minutes is allocated for data entry and positioning the patient.

HRV assessments will be performed prior to functional testing, to avoid the potential impact of physical activity on heart rate measures. This assessment will be performed in a private examination room and will take approximately 30 min.

Physical fitness and function assessments will then be performed. These assessments will be performed in the same order at every assessment, with the most fatiguing assessments performed at the end of the session. The order will be: SLS, TUG, grip strength, 30StS, SCT, gait speed, 400MWT. All tests will be performed by the same investigator at all time points.

This investigator is a licensed physical therapist with experience performing functional tests in medically involved or functionally limited populations. A secondary tester, blinded to participant group, will be present at all sessions to provide any necessary assistance and insure lack of testing bias. Participants will also be given the activity tracker to assess ADSC, with instructions on how to use the device and how to return the device in one week. The functional assessment period will take approximately 1 hour.

Questionnaire data will be collected using REDCap software. Participants will have two options for completing questionnaire data at each assessment: 1) completion of questionnaire data via emailed REDCap survey at the Health and Wellness Center via provided computer or tablet, 2) completion of printed questionnaires provided at the functional assessment. Data obtained from participants completing printed questionnaires will be entered in the REDCap system by two study investigators independently to insure accuracy, following which hardcopies will be destroyed.

If participants will not receive a standard blood draw as part of their medical care within a one-week window of the visit, they will be transported to the CTRC where the necessary blood draw will be performed.

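### One investigator of unstated blinding performs every functional test, and the blinded second tester has no stated part in the measurement

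*Combined protocol and SAP*

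**What the plan says.** Two people attend each functional assessment (section IV.C, Assessments). Of the first, the plan says: "All tests will be performed by the same investigator at all time points". It describes this person by qualification alone: "This investigator is a licensed physical therapist with experience performing functional tests in medically involved or functionally limited populations". Of the second it says: "A secondary tester, blinded to participant group, will be present at all sessions to provide any necessary assistance and insure lack of testing bias".

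The tests concerned are listed in the same place: "The order will be: SLS, TUG, grip strength, 30StS, SCT, gait speed, 400MWT". Section IV.A names the 400-m walk time as the primary outcome within physical fitness and function and defines it as a timed performance: "The test assesses the time it takes a participant to independently walk 400 meters".

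Allocation is not randomized. Under Group Assignment, eligible volunteers "willing to participate in the exercise intervention will be assigned to the exercise group", and those who cannot commit for practical reasons form the control group. The Data Analysis Plan (section IV.F) compares the groups on change: "Change scores will be calculated as the difference between Visit 2 and Visit 1".

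**The concern.** The plan names testing bias as something to prevent and brings a blinded person to every session for that purpose. It then gives the tests to someone else, whose knowledge of group is not addressed. Watching a test does not blind its result. The result is blinded only if the person who produces the number does not know the group.

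The functional tests are sensitive to this. Most are timed, and all depend to some degree on effort, and so on how the participant is instructed and encouraged. Participants know their group, and testing and training take place at the same centre, so group could easily become known to staff. The plan describes nothing to protect the second tester's blinding either.

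What is at stake is the Aim 2, Hypothesis 1 comparison of fitness and function. Section IV.E acknowledges selection bias and baseline differences but not measurement bias. Adjusting for baseline covariates would not remove it.

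**Working it through.** **1. The plan's own figure.** The only power calculation (section IV.B) concerns hospital length of stay: difference 4 days, SD 3, α = 0.05, and 0.90 read as power. The two-sided normal approximation gives n = 2 × [3 × (1.960 + 1.282) / 4]² = 11.82, rounded up to 12 per group, as stated. It does not bear on this point, because length of stay comes from medical records. The documents give no SD, expected effect or bias estimate for the 400-m walk.

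**2. Who measures, and who is blinded.**

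| | Main investigator | Secondary tester |
|---|---|---|
| Performs the tests | Yes, all tests at all time points | Not stated |
| Times, scores or records | Not stated; the natural reading of performing the tests | Not stated |
| Blinded to group | Not stated | Yes |
| Stated purpose | Testing | Assistance and prevention of testing bias |

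Nowhere do the documents place a blinded person in a measuring role.

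**3. What survives in a change score.** Let b(g,v) be the average error that the tester introduces in group g at visit v. The bias in the between-group difference in change is

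[b(E,2) − b(E,1)] − [b(C,2) − b(C,1)].

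An error that is constant across visits within each group cancels, even if it differs between groups. What remains is error that differs by group and changes between visits. This is plausible. At Visit 1 nobody has trained. By Visit 2 the exercise group has been through the programme, and a tester who knows this has a reason to expect improvement in one group only.

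**4. Illustration of size.** Suppose there is no true effect and the surviving bias is b, in SDs of the change score. The chance that a two-sided 5% two-sample t-test rejects is P(|T| > t₀.₉₇₅), where T is noncentral t with 2n − 2 degrees of freedom and noncentrality b × √(n/2). At n = 15, √(15/2) = 2.739, the degrees of freedom are 28 and the critical value is 2.048. The smaller sizes are the 12 per group in the power calculation and the roughly 11 completers per group at the cited 28% attrition (15 × 0.72 = 10.8).

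| Assumed b | Noncentrality (n = 15) | Rejection, n = 15 | n = 12 | n = 11 |
|---|---|---|---|---|
| 0.1 | 0.274 | 5.8% | 5.6% | 5.6% |
| 0.2 | 0.548 | 8.3% | 7.6% | 7.3% |
| 0.3 | 0.822 | 12.5% | 10.8% | 10.3% |
| 0.5 | 1.369 | 26.2% | 21.6% | 20.1% |

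The plan uses exact permutation tests, which the t-test only approximates. A permutation test gives no protection here, because a measurement shift looks the same to it as a real effect.

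**The case against.** The strongest reply is that the plan already has a safeguard and that the rest is inferred from silence. Much of this stands.

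- A reader might infer that the blinded person is there only to assist. The text does not support that: it calls this person a tester and gives a second purpose, preventing testing bias. The fair criticism is that this purpose is stated without a mechanism.
- A reader might infer that the main investigator is unblinded, or that this person alone instructs, times and records. The documents say neither. The second tester may in practice hold the stopwatch, but the plan does not say so.
- Using one investigator, a fixed test order and change scores removes any tester error that is constant across visits. Group may already be known at Visit 1, so some of the bias could cancel. This narrows the concern to error that changes between visits.
- The bias range is assumed, and at 0.1 SD the error rate is close to nominal.
- This is a non-randomized pilot whose results are to be interpreted cautiously, and selection bias may well be the larger problem.

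These points limit the size and wording of the concern. They do not supply a blinded measurement. Cautious interpretation does not replace one when a blinded person is already in the room.

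**Conclusion.** The concern holds in a limited form. As written, the plan leaves the functional tests without a demonstrably blinded measurement, because its safeguard against testing bias has no stated action on the recorded values. The 400-m walk is affected as the primary outcome for physical fitness and function.

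A reader might go further and conclude that the trial's main result is compromised. The documents do not support that. Aim 1 is feasibility, the sample size rests on length of stay, and both length of stay and readmission are taken from the health record, so this bias does not reach them.

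The size is unknown. The figure of about 6% to 26% false rejection at 15 per group rests on an assumed shift of 0.1 to 0.5 SD of the change score, no true effect, complete data and a t-test approximation. It shows how sensitive the comparison would be. It does not estimate what will happen. If the investigator is in fact blinded, or the second tester already records the results, the plan should say so and most of the concern falls away.

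**What to change.** Amend Assessments in section IV.C as follows:

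1. The blinded secondary tester times, counts or reads and records the 400-m walk and the other functional tests, and these are the analysed values.
2. Instructions and encouragement follow a fixed script, read by the blinded tester where feasible. Independent timing alone would not remove encouragement that differs by group.
3. Participants are asked not to reveal their group during assessments.
4. The licensed therapist stays at the session for conduct and safety, and the plan states whether this person is blinded.

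Both people already attend every session, so no staff are added and the sample size does not change. The cost is brief training and a reliability check for the secondary tester, whose qualifications the plan does not give. Participants will still know their own group, so expectation effects on effort will remain and should be listed with the limitations in section IV.E.
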